### **4.5 EFFICACY ANALYSIS**

Endpoints will be summarized descriptively for the modified ITT analysis population, no statistical modelling will be performed, no statistical hypothesis will be tested.

#### **4.5.1 Primary Efficacy Endpoint**

##### **4.5.1.1 Definition of Primary Efficacy Endpoint**

The primary efficacy endpoint of the study is the change from baseline in the BNSS Avolition/Apathy subscore at Week 12.

The BNSS (Strauss et al 2012) is a 13-item instrument designed for clinical trials and other studies that measure the severity of negative symptoms in six domains (subscales), inclusive of one single-item domain of ‘Distress’ (see [Appendix 3](#)):

- **Blunted Affect** (three items): facial expression, vocal expression, expressive gestures;
- **Alogia** (two items): quantity of speech, spontaneous elaboration;

- **Asociality** (two items): asociality - behavior, asociality - internal experience;
- **Anhedonia** (three items): intensity of pleasure during activities, frequency of pleasure during activities, intensity of expected pleasure from future activities;
- **Avolition/Apathy** (two items): avolition - behavior, avolition - internal experience;
- **Distress** (single item): distress.

All ratings are based on a semi-structured interview with prompts and queries. Items are rated on a 7-point scale, ranging from the symptom being no impairment/normal (0), very slight deficit/questionable (1), mild deficit/mild (2), moderate deficit/moderate (3), moderately severe deficit/moderately severe (4), marked deficit/severe (5) to severe deficit/extremely severe (6). A total BNSS score is calculated by summing the 13 individual items so that the possible total score ranges from 0 to 78. Subscores are calculated by summing the individual items within each domain (subscale). The primary efficacy endpoint, the change in avolition/apathy subscale ranges from 0 to 12.

Higher scores indicate more negative symptoms. Hence negative values for change from baseline indicate improvement.

In study **Part A**, the BNSS is assessed by an approved remote centralized rater at Week -4, Day 1 (Baseline), Day 14, Day 28, Day 42, Day 56, Day 70, Day 84/EOT and Day 112 (FU). All assessments will be assigned to analysis study days according to the following table.

Assessment Days	Assigned Analysis Study Day
>88 or >4 days after last study medication	FU, will not be included in statistical analysis
78-88	84
64-77	70
50-63	56
36-49	42
22-35	28
2-21	14
-2-1	1
<-2	-35, will not be included in statistical analysis

Descriptive summary statistics and listings will be presented for the BNSS **Avolition/Apathy subscore** by visit and treatment arm for the modified ITT analysis population by treatment arm to which participants were randomized. The same descriptive summary statistics and will be presented for the change from baseline in BNSS Avolition/Apathy subscore.

#### **4.5.2 Secondary Efficacy Endpoints**

Descriptive summary statistics will be presented for all secondary efficacy endpoints by visit and treatment arm for the modified ITT analysis population by treatment arm to

which participants were randomized. The same descriptive summary statistics and will be presented for the change from baseline.

Descriptive summary statistics will include the number of patients contributing to the summary statistic as well as the mean, median, lower and upper quartile, standard deviation, minimum and maximum.

In general, if at least one item score is missing or not ratable, the total/factor/subscale scores that include the item will be set to missing.

#### **4.5.2.1      CGI-S and CGI-I Overall and Negative Symptoms**

The CGI rating scales are tools used to evaluate both the severity of illness and change from baseline. It provides an overall clinician-determined summary measure that takes into account all available information, including a knowledge of the participants' history, psychological circumstances, symptoms, behavior, and the impact of the symptoms on the participant's ability to function.

##### **CGI-S and CGI-S NS**

The CGI-S is a 7-point scale ranging from 1 (normal, not at all ill) to 7 (among the most extremely ill patients) (see [Appendix 5](#)). On the scale, the value 0 corresponds to 'Not assessed', which will be excluded from the analyses. The values 1 to 7 will be transformed into the 0 to 6 range prior to statistical analysis. The CGI-S is an absolute measure assessing how mentally ill the participant is at the time of the assessment.

Smaller values indicate less severity of illness. Hence negative values for change from baseline indicate improvement.

The CGI-S NS is very similar to the CGI-S and will be analyzed in the similar manner.

In study **Part A** CGI-S along with CGI-S NS will be evaluated at Day 1 (baseline), Day 14, Day 28, Day 42, Day 56, Day 70, Day 84 /EOT, Day 112 (FU) by an experienced clinician. All assessments will be assigned to analysis study days as described for the primary endpoint.

The CGI-S and CGI-S NS scores and change from baseline will be summarized.

##### **CGI-I and CGI-I NS**

The CGI-I, a 7-point scale rating, is used to assess the clinical changes as compared to symptoms at baseline. The scale requests an assessment by how much, compared to baseline, the condition of the participant has changed (see [Appendix 5](#)). Values range from 1 (very much improved) to 7 (very much worse) where the value 0 corresponds to 'Not assessed', which will be excluded from any analyses. The values 1 to 7 will be centered prior to analysis so that 0 becomes 'no change' and the values -3 and +3 correspond to 'very much improved' and 'very much worse', respectively.

The CGI-I NS is very similar to the CGI-I and will be analyzed in the similar manner.

In study **Part A** CGI-I along with CGI-I NS will be evaluated at Day 14, Day 28, Day 42, Day 56, Day 70, Day 84 /EOT, Day 112 (FU) by an experienced clinician. All assessments will be assigned to analysis study days as described for the primary endpoint.

The The CGI-I and CGI-I NS scores will be summarized. There is not baseline value for CGI-I and CGI-I NS, therefore no change from baseline can be derived.

#### **4.5.2.2 PANSS Total and Symptom Factor Scores**

PANSS assessments are performed by an approved remote centralized rater.

The PANSS is a 30-item clinician-rated instrument for assessing positive, negative and other symptoms in patients with schizophrenia (see [Appendix 4](#)). The symptoms are rated on a 7-point scale capturing absent to extreme psychopathology, and the tool demonstrated sensitivity to effects seen with medication. The assessment for each of the 30 items is to allow calculation of a total score describing overall symptomatology as well as the factor scores (the classification of symptoms into five factors: negative symptoms; positive symptoms; disorganized thought; uncontrolled hostility/excitement; and anxiety/depression) which are calculated for each factor. Additionally, negative and positive symptom factor scores according to Marder (PANSS-NSFS, PANSS-PSFS, see Table 5 in protocol V2) are used.

Each item of the PANSS is rated on a 7-point scale on the basis of the following anchors: 1 = Absent, 2 = Minimal, 3 = Mild, 4 = Moderate, 5 = Moderately Severe, 6 = Severe, and 7 = Extreme. For the analyses of PANSS data, the scores will be transformed into 0 to 6 points with "Absent" expressed as 0.

Higher scores indicate more positive and negative symptoms. Hence negative values for change from baseline indicate improvement in symptoms.

In study **Part A**, the PANSS is assessed at Week -4, Day 1 (Baseline), Day 14, Day 28, Day 42, Day 56, Day 70, Day 84/EOT, Day 112 (FU). All assessments will be assigned to analysis study days as described for the primary endpoint.

The PANSS total factor and symptom factor scores and change from baseline will be summarized.

#### **4.5.2.3 BNSS Total and Subscores**

See section 4.4.1.1.

The BNSS total and subscores (other than Avolition/Apathy) and change from baseline will be summarized.

#### **4.5.2.4 DPAS Scores**

The DPAS is a 15-item, patient-reported assessment that evaluates expectations of failures or self-defeating beliefs related to prior failed experiences as well as illness on a 7-point Likert scale ranging from disagree totally (1), disagree very much (2), disagree slightly (3), neutral (4), agree slightly (5), agree very much (6), to agree totally (7) (for items see [Appendix 6](#)). For the analyses of DPAS data, the scores will be transformed into 0 to 6 points with “disagree totally” expressed as 0.

Higher scores indicate higher expectation of failure or self-defeating beliefs. Hence negative values for change from baseline indicate improvement.

In study **Part A** DPAS is assessed at Day 1 (baseline), Day 42, and Day 84/EOT. All assessments will be assigned to analysis study days according to the following table:

Assessment Day	Assigned Study Day
>88 or >4 days after last study medication	FU, will not be included in statistical analysis
64-88	84
2-63	42
-2-1	1
<-2	-35, will not be included in statistical analysis

The DPAS sum score and change from baseline will be summarized.

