8.1.3 Efficacy Assessments to be Completed by the Participant

8.1.3.1 Defeatist Performance Attitude Scale

The DPAS is a 15-item, patient-rated assessment that evaluates expectations of failures or self-defeating beliefs related to prior failed experiences as well as illness on a 7-point Likert scale ranging from totally agree (1) to totally disagree (7). Previous research suggests a correlation in defeatist beliefs (e.g., "People will probably think less of me if I make a mistake" or "People who have good ideas are more worthy than those who do not") and negative symptoms in schizophrenia (Grant and Beck 2009). This scale takes approximately 10 minutes to complete. It will be completed by the participant during site visits.

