## **4. STATISTICAL METHODS**

The final analysis of data from the trial will be performed separately for **Part A** and **Part B**. This TDSA describes the analyses for **Part A**.

Data for study **Part A** will be listed and summarized descriptively. No formal hypothesis test will be performed.

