#### **4.7 MISSING DATA**

Generally, in summaries, all data from the respective analysis population regardless of completeness by Week 12 will be included; participants who have taken the study medication or have visited the sites only partially will be included in the summaries. No imputation will be applied for missing data will be applied.

For all rating scales, if any item score contributing to the total/factor/subscale score is missing, then the total/factor/subscale will be set to missing.

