## Appendix 6 DPAS Questions

1. It is difficult to be happy unless one is good-looking, intelligent, rich and creative.
2. People will probably think less of me if I make a mistake.
3. If I do not do well all the time, people will not respect me.
4. Taking even a small risk is foolish because the loss is likely to be a disaster
5. If a person asks for help, it is a sign of weakness.
6. If I do not do as well as other people, it means I am an inferior human being.
7. If I fail at my work, then I am a failure as a person.
8. If you cannot do something well, there is little point in doing it at all.
9. Making mistakes is fine because I can learn from them.
10. If I fail partly, it is as bad as being a complete failure.
11. People should have a reasonable likelihood of success before undertaking anything.
12. If I don't set the highest standards for myself, I am likely to end up a second-rate person.
13. If I am to be a worthwhile person, I must be truly outstanding in one major respect.
14. People who have good ideas are more worthy than those who do not.
15. If I ask a question, it makes me look inferior.

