## Appendix 8 Fagerström Nicotine Dependence Test (FTND) Scoring

How Long	0 = After 60
After Waking	minutes
For First	1 = 31-60 minutes
	2 = 6-30 minutes
	3 = Within 5 minutes
Difficult to	0 = No
Refrain	1 = Yes
Hardest	1 = The first
Cigarette to	in the morning
Give Up	0 = Any other
No. of	0 = 10 or less
Cigarettes per	1 = 11-20
Day	2 = 21-30 3 = 31 or more
More Just	0 = No
After	1 = Yes
Awakening	
Smokes When	0 = No
ill and	1 = Yes
Bedbound?	

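### The SAP has no reverse-scoring rule for DPAS item 9, so as written that item enters the sum with the wrong sign; the protocol and SAP response anchors also run in opposite directions

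*SAP*

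**What the plan says.** SAP 4.5.2.4 describes a 15-item patient-reported scale with a "7-point Likert scale ranging from disagree totally (1), disagree very much (2), disagree slightly (3), neutral (4), agree slightly (5), agree very much (6"), ending at total agreement for 7. The scores are shifted to run from 0 to 6, with total disagreement as 0 and no exception for any item. The section then fixes the direction: "Higher scores indicate higher expectation of failure or self-defeating beliefs", so a negative change is an improvement. The reported quantity is the sum: "The DPAS sum score and change from baseline will be summarized".

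Appendix 6 lists the wording of the 15 items without a scoring key. Item 9 reads "Making mistakes is fine because I can learn from them".

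The only rule that covers every scale is in SAP 4.7 and concerns missing items: "For all rating scales, if any item score contributing to the total/factor/subscale score is missing", the total is set to missing. Elsewhere the SAP does give item-level scoring, in Appendix 8 ("Fagerström Nicotine Dependence Test (FTND) Scoring").

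Protocol 8.1.3.1 describes the same instrument as a "7-point Likert scale ranging from totally agree (1) to totally disagree (7"), which is the reverse of the SAP numbering. Both documents name change from baseline in DPAS as a secondary endpoint. SAP section 4 limits Part A to listings and descriptive summaries: "No formal hypothesis test will be performed".

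**The concern.** Someone who agrees with item 9 is giving the non-defeatist answer. Under the SAP recode that person receives the maximum of 6 points on the item, and someone who rejects it outright receives 0. The item therefore runs against the direction that the SAP assigns to the total. Nothing in 4.5.2.4, Appendix 6 or 4.7 corrects this.

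What is at stake is the size of a secondary endpoint's change score. If item 9 moves with the other items, the change is diluted; if it moves against them, the change is inflated; if it stays put, the change is unaffected.

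The anchor conflict is a separate matter. The SAP sets the analysis direction by response label, so the plan itself does not invert the result. But data captured with the protocol's numbering need a different conversion from data captured with the SAP's, and neither document says which numbering the data carry.

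**Working it through.** The documents give no DPAS figure (range, standard deviation or power) to reproduce. The check is scoring arithmetic.

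**Inputs**
- 15 items, each coded 0 to 6, total disagreement = 0 (SAP 4.5.2.4).
- Higher sum = more defeatist; negative change = improvement (SAP 4.5.2.4).
- Item 9 keyed opposite to the other 14 (SAP Appendix 6).

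**Error in one total.** Let x be the transformed item 9 score. The SAP adds x; a sum that matches the stated direction needs 6 - x. The error is x - (6 - x) = 2x - 6, which runs from -6 (x = 0) to +6 (x = 6).

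**Error in a change.** From x1 to x2 the error is 2(x2 - x1), which runs from -12 to +12. The extremes require a patient to move from one end of item 9 to the other.

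**Extreme answer patterns**
- Fully non-defeatist: 14 × 0 + 6 = 6 as written; 0 with item 9 reversed.
- Fully defeatist: 14 × 6 + 0 = 84 as written; 14 × 6 + 6 = 90 with item 9 reversed.
- Span: 84 - 6 = 78 instead of 90.

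**Change when the other 14 items each improve by one point (-14)**

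| Item 9 | As written | Item 9 reversed |
|---|---|---|
| also improves by 1 (x rises by 1) | -14 + 1 = -13 | -14 - 1 = -15 |
| unchanged | -14 | -14 |
| worsens by 1 (x falls by 1) | -14 - 1 = -15 | -14 + 1 = -13 |

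Under the uniform shift in the first row the raw change keeps 13/15 = 0.867 of its size, a loss of 13%.

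**Standardized effect.** The documents contain no item data, so this step assumes a uniform shift, equal item variances and one common correlation r between correctly keyed items. In units of one item's variance:
- variance of the correct sum: 15 + 15 × 14 × r = 15 + 210r;
- variance of the sum as written, where the 14 pairs involving item 9 change sign: 15 + 14 × 13 × r - 2 × 14 × r = 15 + 154r.

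The fraction of the standardized effect kept is (13/15) × √[(15 + 210r)/(15 + 154r)]:
- r = 0: 0.867
- r = 0.1: (13/15) × √(36/30.4) = 0.943
- r = 0.3: (13/15) × √(78/61.2) = 0.978
- r = 0.5: (13/15) × √(120/92) = 0.990

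**Anchors.** Let y be the raw response from 1 to 7. With SAP numbering the 0-to-6 score is y - 1. With protocol numbering it is 7 - y. Subtracting 1 from protocol-numbered data would turn each item score v into 6 - v. A sum S would become 15 × 6 - S = 90 - S, and every change would switch sign.

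**The case against.** The strongest case on the other side is about weight. Part A stopped at 27 randomized patients, reports DPAS descriptively without modelling, and bases no decision on it. One item in 15 is affected. With correlations from 0.1 to 0.5 the standardized effect keeps 94% to 99% of its size, and under the uniform-shift assumption both arms are attenuated by the same factor, so the direction of a between-arm difference is unchanged. All of this stands as a limit on the consequences. It does not make the derivation right, and Part A reports the raw change, the quantity that loses 13% under a uniform shift.

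It can also be said that reversal may be built into the electronic or paper form, and that the stated direction of the score is a cue for a programmer to reverse item 9. Both are possible. Neither is written down, and the explicit recode by label points the other way.

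On the anchors, the SAP was written against protocol version 2 (SAP 4.5.2.2 and Appendix 1), whose DPAS anchors cannot be checked here, while the protocol at hand is version 6. The SAP's label-based rule is clear. What stands is an inconsistency with a programming risk, not an inverted analysis.

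Finally, the contrast with the nicotine scale proves little. That scale needs a key because its response formats differ by item, and the SAP also lists the BNSS and PANSS items without one. The point rests on the wording of item 9.

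**Conclusion.** The concern holds. Applied exactly as written, SAP 4.5.2.4 gives item 9 the wrong sign relative to the section's own statement of direction, unless the captured data are already reversed, which the documents do not say.

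One visit total can be wrong by up to 6 points and a change by up to 12. The 13% loss in raw mean change assumes that all items, including item 9, shift equally; there is no error in change if item 9 does not move. The loss in standardized effect is small under the assumed correlations, 13% at most (r = 0).

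In Part A the effect is confined to descriptive summaries of a secondary endpoint; no test, alpha or sample size is touched. Part B has a separate plan that is not available, so whether it shares the gap is unknown. Protocol 9.4.2 foresees models similar to the primary one for DPAS change, so a shared gap would reach modelled estimates. The anchor mismatch is real but does not by itself invert the planned score.

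**What to change.** First confirm the response numbering, and any reversal of item 9, on the form actually used; protocol Appendix 1, section 2.1.2 allows both electronic and paper capture.

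Then add one sentence to SAP 4.5.2.4: item 9 is scored as 6 minus its transformed score before summing, giving a range of 0 to 90. If the data turn out to be reversed at capture already, the sentence should say that instead, so that the plan carries one unconditional rule.

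Align the anchors in protocol 8.1.3.1 and SAP 4.5.2.4 with the form, and check that the separate Part B plan scores DPAS the same way.

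The cost is one SAP sentence, one line of derivation code and one anchor correction. No new data are needed.

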#### **Descriptive Summaries:**

Overall and separately for all levels of the factors 'reward' (levels 3, 5, or 7) and within each patient, the percentage how often the high effort task was selected will be derived. These percentages obtained for each patient will then be summarized by treatment per assessment. The summaries will show the mean, median, lower and upper quartile as well as minimum and maximum.

#### **4.5.3.2 Reinforcement Learning Working Memory (RLWM) task**

The RLWM task assesses the ability to learn from positive reward and establish corresponding mental value representations, functions that are deficient in patients with negative symptoms. The RLWM task is assigned to the participants to complete.

#### **Task Description:**

**Learning Phase (LP):** To complete the RLWM task, at the learning phase, participants have to learn to select one out of three button presses for each **stimulus (=image)**: on each presentation (trial), a single stimulus is presented to which participants can respond with one of three responses (button presses). Participants have to learn over time which of those responses is the correct one for each stimulus, based on the binary deterministic feedback they receive.

The stimuli are presented in **blocks**. The number of stimuli in the block to be learned at a time ranges from 2, 3, 4, 5, 6. There are two blocks of size  $n_s = 2$  (i.e., two blocks containing two stimuli each), three blocks of size  $n_s = 3$ , two blocks of size  $n_s = 4$ , three blocks of size  $n_s = 5$ . The total number of blocks is 10. The stimuli in each block correspond to a different category of images (e.g., sports, fruits, places, etc.) leading to a

total of  $2 \times 2 + 3 \times 3 + 2 \times 4 + 3 \times 5 = 36$  different stimuli. Within each block, stimuli are presented in a pseudo-randomly intermixed order, with 10 presentations of each stimulus within a block, i.e., a total of 360 presentations within a session. When participants select the incorrect action for a stimulus, they receive feedback indicating they have won 0 points, but if they select the correct action, they obtain a reward of 1 or 2 points. Each stimulus has a **fixed** probability  $q$  of resulting in 2 (vs. 1) points of reward for correct actions ( $q$  is 0.25, 0.50, and 0.75); the probabilities are pre-assigned to counterbalance across set sizes and other factors. The correct action is always correct and the incorrect one is always incorrect. The participant would not know the probability  $q$  of receiving 2 points (rather than 1 point) in case of a correct answer. Although the participants have no control over the reward values, their striatal reinforcement learning system is expected to learn to represent higher expected reward values for those stimuli associated with higher probability of two points, which can be assessed in the test phase.

**Test Phase (TP):** After the learning phase, participants face a test phase, in which they are presented with **pairs of stimuli** they previously encountered. They are asked to choose the stimulus that they perceive to have given them most points in the learning phase. Instead of selecting the response that had been 'correct' for each of the individual stimuli, in this phase participants are asked to select among pairs of stimuli and to indicate their preferences (more likely to choose ones they think had led to more points). They receive no reward. The test phase includes 156 trials, i.e., 156 pairs of stimuli. These 156 pairs are selected among all 1176 (49 choose 2) possible pairs. The selection is based on the actual responses of the participant in the learning phase and done in a way to ensure that sufficient pairs with a range of 'Value Differences' but also 'Value Means' (see below) are included. Participants are more likely to select the more rewarding stimuli, and they do so more reliably as the difference between their reward values grows. This test also allows us to assess whether participants perform better either **at choosing the most rewarding stimuli or at avoiding the least rewarding stimuli, when each of these are paired with neutral stimuli**. Such difference in performance in these two situations is related to striatal dopaminergic measures in various studies.

With lower set sizes, participants can rely on (fast but subject to decay in time and capacity-limited) working memory (WM). As set size exceeds their WM capacity, they have to rely on incremental (slow, cumulative learning) reinforcement learning (RL). The paradigm can thus isolate WM from RL processes that are striatal dependent.

---

 As an example, there are 2 blocks of size 2 each, leading to a total of 4 different images across these two blocks. Among these 4, two each may be assigned probability 0.25, 0.50, and 0.75; the remaining two may be assigned either of the three. Similarly, there are 3 blocks of size 3. Across the 9 images, each probability is assigned to three images, but not all images from the same block need to have distinct probabilities.

Assessment schedule are at Weeks 1 (baseline), 2, 6, 12 for both Parts A and B. No assessment is planned for Screening or Follow-up.

